Study participants will be assigned a permanent unique study ID number upon enrollment, which will be the only identifier associated with any of the survey data and addresses. A key linking personal identifying information (name, other household members who are taking the survey, and address) with study ID number will be kept in a separate encrypted data file stored secured research shared drives (i.e. not on personal computers that are vulnerable to theft) in the study's data coordinating centers in either the GE NCDC or the AM NIH and then transferred to the study's data coordinating center at Emory University Rollins School of Public Health. Files will be accessed only on an as needed basis for the conduct of the study. Physical security of the data center's servers and files is maintained with double-locked keyed doors during all hours. Only authorized persons are allowed access. Identifying information will be kept in a secured folder in encrypted version for the duration of the study data management purposes. Once all phases of the study have been conducted, the identifiers will no longer be needed and will be deleted from the data sets.

L. INFORMED CONSENT

Regional and local public health and community-based organization leaders will complete a capacity assessment. This capacity assessment survey will be used to ensure comparability across intervention and comparison communities. This will be completed prior to conducting consent for other aspects of the study. Statements of consent for each of the data collections are included in this application.

We are asking for waiver of documentation of consent for the coalition member survey. The primary mode of data collection for this survey will be via an online platform such as SurveyMonkey or SurveyGizmo. However, to ensure a high response rate, the two backup methods of data collection for those with unreliable internet access are mailing a PDF of the survey and conducting the survey via a phone call, both of which would make obtaining documentation of consent burdensome for the participants. Since the survey does not entail more than minimal risk, we believe a waiver of documentation of consent is appropriate.

M. PLANS TO INFORM PARTICIPANTS OF NEW FINDINGS

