established in 1994 to improve and strengthen the processes for managing communicable and non-communicable diseases, reorienting the system on preventive services. The Department for Regional Public Health Management within the NCDC, directed by **[name] (co-I)**, oversees the 68 local public health centers, which are municipal public units. These centers manage programs regarding communicable disease prevention, chronic disease management, and healthy living, as well as measures and activities to meet the health needs of the population living in particular areas. **Public health services in AM** evolved from the 1992 Law on Sanitary-Epidemic Safety. In 2002, the country's sanitary and epidemiological services were reorganized as the State Hygiene and Anti-epidemic Inspection under the Ministry of Health. It consists of a headquarters office and seven operations offices in Yerevan as well as 10 regional offices and several additional local public health centers and other facilities within the local municipalities. In the proposed study, directors of these local public health centers will serve as or identify key leaders to engage in the coalition trainings and lead coalition activities.

*Our study will define a “community” as a distinct municipality, given the division of communities based on the coverage area of the local public health centers. We will include communities with small to medium populations and local public health centers with sufficient capacity to engage in the proposed research. Our partners in GE and AM have identified 14 municipalities within each country fitting these criteria, with populations ranging from ~6,000 to 90,000. An example of GE municipalities and their populations, distances from Tbilisi, and budgets are listed in **Appendix A**. After confirming interest with local health center directors, we will form matched pairs in each country based on population size, region, and local economy and then randomly select one from each pair as an intervention community and the other as a control. We will use block randomization by country. Randomization will occur after completion of the baseline population-level survey.*

[figure not shown]
Condition Description. In brief, all 28 communities (14/country) will participate in the population-level tobacco survey at baseline and follow-up. Within each country, 7 communities will be randomized to the intervention condition and 7 to the control condition (i.e., 14 communities/condition).

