In addition to engaging partners, steps for policy change include documenting local problems (e.g., observations, key informant interviews), formulating policies (e.g., developing/sharing model policies for different sectors), building awareness (e.g., creating promotional materials, holding awareness and earned media events, developing press releases to media, using social media), and persuading decision-makers (e.g., meeting with decision-makers, encouraging/supporting surveys to assess support for policy change, finding/sharing personal stories, making health/cost savings arguments).^{95,96} We will remain sensitive to the four step policy-making process:⁹⁵ 1) *formulation* refers to identifying potential solutions or approaches (e.g., drafting policies/action plans); 2) *enactment* includes identifying a champion or sponsor and formally approving the policy or action; 3) *implementation* involves developing a plan for implementation, communicating the policy or action, training relevant staff or volunteers, and actually conducting the required activities and tasks; and 4) *maintenance* refers to ensuring sustained implementation and enforcement of the changes.

Annual Coalition Meetings. In Years 3 to 5, the coalition members will attend annual meetings with the research team in order for local coalition leaders and members to problem-solve challenges and share success stories. Training topics will be determined based on needs identified by grantees (e.g., use of media in tobacco control, other topics relevant to the policy change process). In Year 5, the coalitions will be offered the opportunity to present their research findings within the larger regional meeting open to a broader constituency.

Technical Assistance (TA) Process. TA will be provided by the GE NCDC, AM NIH, and Emory research teams and will consist of monthly check-in e-mails or calls to ensure accountability and assist with challenges that arise. Standardized procedures for documenting coalition meetings and activities will be implemented.

Data Collections: One data collections will address Aim 1, and two data collections will address Aim 2.

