Assessment 1: Population-level Survey (addressing Aim 1). The GE NCDC and AM NIH will conduct cross-sectional population-level surveys in Year 1 (baseline) and in Years 4/5 (follow-up) in the intervention and control communities. A multi-stage, clustered sample design will be used to select 50 participants within each municipality. Eligible participants will be adults aged 18-65. The most recent census data for each country and the respective municipalities will be used to establish the sampling frame. The “random walk” method will be used for selecting the households within each municipality. For households with more than two eligible adults, the “Kish method” used in the WHO’s STEPS surveys will be applied.¹⁰⁴ In the KISH method, all eligible participants from the household are first ranked according to age in decreasing orders (males followed by females). Then, participants are selected using the KISH table identifying the last digit of household and number of eligible participants.¹⁰⁴ Using this approach, our prior research resulted in an 89.9% response rate.²⁰

Assessments 2 & 3: Coalition Assessment (addressing Aim 2): Mixed methods will be used to measure constructs in our conceptual model related to Aim 2. Coalition assessments conducted by TSMU/AUA will include: 1) coalition member surveys; and 2) semi-structured interviews with coalitions leaders and staff. More detail on specific roles are outlined in the sections below.

We plan to enroll a total of 4,000 participants for all of our assessments over the various data collection periods.

D. MEASURES

Table 1. Coalition Activities by Year

| Year | Coalitions Activities |
|------|--|
| 1 | 
 1. Attend situational assessment training 2. Begin situational assessment: 
 -summarize population data -review tobacco-related data (new, existing) -conduct ≥10 key informant interviews |
| 2 | 
 1. Complete situational assessment 2. Form a multi-sectoral community coalition 3. Develop, begin to implement action plan to promote policies in worksites, restaurants |
| 3 | 
 1. Continue to implement action plan |
| 4 | 
 1. Continue to implement action plan 2. Plan for sustainability |

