Assessment 1: Population-level Survey. Data will be collected in person by NCDC/NIH staff using hard copy and/or technology-assisted procedures. The survey will assess the following primary and secondary outcomes and covariates.

Primary Outcome. Measures of individual-level of *changes in SHS exposure* will be adapted from the Global Adult Tobacco Survey (GATS)¹⁰⁵ and CDC's National Adult Tobacco Survey (NATS).¹⁰⁶ The GATS assesses SHSe by first asking about locations they came into contact with in the past 30 days (e.g., workplace, government buildings/offices). Follow-up questions for those who had been in contact with each location then assess SHSe in each location (e.g., "Did anyone smoke inside of any government buildings or government offices that you visited in the past 30 days?") The GATS assesses SHSe in the home by asking, "How often does *anyone* smoke inside your home? Would you say daily, weekly, monthly, less than monthly, or never?" While we will administer these measures in order to facilitate cross-country comparisons, we will also create a SHSe index by assessing *frequency* of SHSe in the past week, adapting items from CDC's NATS, which assess number of days in the past 7 days one was exposed to SHS in the home, in vehicles, at work, in indoor public places, and in outdoor public places.¹⁰⁶ As the impact of coalition activities on SHSe may be modest, a continuous measure assessing a larger outcome range provides greater sensitivity for detecting changes.

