Power Calculation. We powered the CRCT on the *primary outcome of SHSe* per the population-level survey. We determined power using closed equations to calculate the minimum number of clusters for a CRCT for a specific effect size and intra-class correlation (ICC) and used Moerbeek and Teerenstra's formulas for CRCTs with fixed cluster sizes.¹⁰⁷ We assumed a conservatively high ICC of 10% (especially for a matched-pair design), 50 participants per cluster, and small to medium effect size (d=.35).¹⁰⁸ Calculations indicated that 28 communities provided adequate power. If the ICC is lower, we are powered to detect smaller effects (.27 or .24 if the ICC's are 5% or 3%, respectively).¹⁰⁹ Our sample size is larger than one in a comparable study.¹¹⁰

Analyses. First, we will assess key variables for normality of distributions. For both baseline and follow-up samples, we will use PROC GLIMMIX to compare sociodemographics in intervention and control conditions as well as the two countries. We will use multilevel modeling to assess intervention impact. Multilevel modeling allows to model both individual- and community-level variances, predictors, and cross-level interactions simultaneously.¹¹¹⁻¹¹³ This allows for unbiased estimates of effects. For the primary outcome of SHSe, we will assess intervention impact using a two-level model adjusting for individual- and cluster-level covariates while

accounting for unmeasured differences between clusters. Models will be built sequentially, adding first individual- and then community-level covariates including country and baseline means, and finally intervention assignment.¹¹⁴ Random effects for the intercept and intervention impact will be modeled in all models. This allows for differences in the outcome across communities, both due to the intervention and due to other unmeasured factors. For secondary outcomes, multilevel models with the appropriate link function (i.e., linear for continuous outcomes, Poisson for count outcomes, binary for dichotomous outcomes) will be built similarly to those for the main outcome. Additional analyses will model cross-level interaction effects (i.e., community-level moderators of the intervention effect). [name], from George Washington University, will lead many of the analyses.

For Aim 2: Coalition Assessment

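### Does starting Kish selection only above two eligible adults leave respondent selection undefined in the primary-outcome survey?

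*Combined protocol and SAP*

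**What the plan says.** Section C (Assessment 1: Population-level Survey) sets out cross-sectional surveys at baseline and follow-up, with 50 adults aged 18-65 per municipality and households found by random walk. Within-household selection by the Kish method is called for "For households with more than two eligible adults". The sentence on the Kish table speaks of participants in the plural. The number interviewed per household is not given.

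Section K (Confidentiality) describes a separate linking key that holds, among other items, "other household members who are taking the survey". It also assigns a study ID, "which will be the only identifier associated with any of the survey data and addresses".

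Section H (Aim 1) bases power on a single clustering term: "We assumed a conservatively high ICC of 10" per cent, with 50 participants per cluster, d = 0.35 and 28 communities. For the primary outcome, "we will assess intervention impact using a two-level model" is the stated approach, so there is no household level.

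On timing and staffing, Section C states "Randomization will occur after completion of the baseline population-level survey". Section D adds "Data will be collected in person by NCDC/NIH staff", and the Technical Assistance paragraph of Section C says "TA will be provided by the GE NCDC, AM NIH, and Emory research teams".

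**The concern.** A one-adult household needs no selection rule, and a household of three or more has one. A household of exactly two seems to fall between them, in the survey that supplies the primary outcome. Two practices could fill the space.

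- **Both adults are interviewed.** Their answers will be correlated, and neither the single-ICC power calculation nor the two-level model has a term for that.
- **One adult is taken at the interviewer's discretion.** The respondent mix by sex and employment could then drift. Section A reports smoking in 57.7% and 52.3% of men against 5.7% and 1.5% of women, so who answers matters. The follow-up wave comes after randomization and is fielded by staff of agencies that also support the intervention coalitions, so any drift could in principle differ by arm.

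At stake would be some precision under the first practice and possible selection bias under the second.

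**Working it through.** **Reading the sections together.** If one person per household were intended, random selection would have to start at two eligible adults, and a key listing co-resident respondents would have no purpose. If up to two are intended, selection starts at three, which is the threshold in Section C, and the key in Section K has a use. Only the second reading fits both sections without treating either as a slip. It is an inference, because no section states it.

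**Inputs from Section H.** m = 50 per municipality, 14 municipalities per arm, and (ICC, d) = (0.10, 0.35), (0.05, 0.27), (0.03, 0.24).

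**Assumptions.** Two-sided alpha 0.05 (none is stated for Aim 1), normal approximation, and no gain from matching or covariates. The share of interviews that belong to a household pair is s = 0.5-1.0. The within-household correlation on the exposure index is r = 0.3-0.7.

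**The plan's own position, without pairing.**

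- DEFF = 1 + 49 × ICC
- SE = √(2 × DEFF / 700), where 700 = 50 × 14
- Power = Φ(d/SE − 1.96)

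At ICC 0.10: DEFF = 5.90, SE = 0.1298, d/SE = 2.696, power = 76.9%. Section H says only that power is adequate, so there is no stated percentage to reproduce.

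**With household pairs.** Each paired respondent has one partner at correlation r instead of ICC:

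- DEFF = 1 + s × r + (49 − s) × ICC

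Mild case at ICC 0.10 (s = 0.5, r = 0.3): 1 + 0.15 + 4.85 = 6.00. Extreme case (s = 1, r = 0.7): 1 + 0.70 + 4.80 = 6.50.

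| ICC, d | DEFF, no pairs | DEFF, pairs | Power, no pairs | Power, pairs | Loss (points) |
|---|---|---|---|---|---|
| 0.10, 0.35 | 5.90 | 6.00-6.50 | 76.9% | 76.2-72.9% | 0.7-4.1 |
| 0.05, 0.27 | 3.45 | 3.58-4.10 | 77.6% | 76.2-70.4% | 1.5-7.3 |
| 0.03, 0.24 | 2.47 | 2.61-3.14 | 81.5% | 79.4-71.7% | 2.1-9.8 |

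At ICC 0.10 the effective number of interviews per municipality goes from 50/5.90 = 8.5 to between 50/6.00 = 8.3 and 50/6.50 = 7.7. A middling case (s = 0.8, r = 0.4) gives DEFF 6.14 and power 75.3%, a loss of 1.6 points. The upper end of each range needs every interview to be in a pair and r = 0.7 on an index in which three of the five settings lie outside home and vehicle.

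**Validity.** Arm is assigned to municipalities, and every household lies within one municipality. Household correlation adds to the variance of the municipality means, and the community random effect picks that up when the arms are compared. The standard error therefore reflects the pairing without a third level.

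**Cost of one respondent per household.** With pairs, 50 interviews need 50 − 25s households, which is 37.5 at s = 0.5 and 25 at s = 1. One per household needs 50. The difference is 12.5-25 per municipality, or 350-700 over 28 municipalities in each wave. It also makes selection probabilities more unequal. I assumed three mixes for the percentage of households with 1, 2, 3 and 4 eligible adults: (20, 40, 25, 15), (15, 35, 30, 20) and (10, 60, 20, 10). Under these, the weighting factor 1 + CV² is 1.12-1.17 with one respondent per household and about 1.08 with up to two. Section H plans no weights in either case.

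**The case for a change.** The strongest case for a change is that the plan should not depend on inference. The number of respondents per household is not stated, and reading the threshold as a slip for more than one adult remains possible. Stating a rule would take one phrase. Follow-up interviewers are not described as blinded and come from agencies that assist the coalitions. As an illustration, if two-adult households supplied 40-60% of interviews (assumed), each 10-point arm difference in who is picked there would move the sample mix by 4-6 points. Once identifiers are deleted, household pairing could no longer be examined.

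Part of this stands: the number is unstated, and a report of the trial should give the rule that was used. The rest is weaker.

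- Discretionary choice is not described anywhere, and the 10-point difference is invented for illustration.
- Baseline precedes randomization, so arm-related choice cannot arise there.
- Unblinded interviewers could affect household substitution or non-response under any within-household rule, so that risk does not turn on the Kish threshold.
- Section D aims for roughly equal numbers of men and women. Section H compares sociodemographics between conditions in both waves, and Section I trains staff in sampling and protocol adherence. These do not supply the missing rule, and employment is not a named covariate, but a measured shift in mix would be seen.
- Section K is a confidentiality clause. It does not bar a non-identifying household code, and the key is kept while the study's data are being managed.

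**Conclusion.** No change to the plan follows. The unstated number is a gap in reporting detail that Sections C and K together fill sensibly: up to two adults per household, with Kish selection when there are more. On that reading the arm comparison is sound. The omitted household clustering costs about 1-4 power points at the ICC the plan uses, which it calls conservatively high. Losses of 7-10 points appear only at the lower ICCs combined with the most extreme pairing assumptions. These sizes rest on the assumed alpha, pair share and within-household correlation.

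The possible bias from interviewer discretion is speculative and cannot be sized from the documents. The obvious remedy, one respondent per household, is a trade-off and no clear gain. It needs more households and makes selection probabilities more unequal. Section C also refers to events since the study began, so baseline may already have been collected, and if it took two per household a switch would make the waves less comparable.

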We propose to conduct a matched-pairs community randomized controlled trial (CRCT) to examine the impact of coalitions promoting smoke-free air policies on individual SHSe. In doing so, we will be able to test the CCAT²¹ and examine the characteristics and processes of community coalitions that effect change. The Emory team will lead the oversight of the research design and execution of all components of the research. The GE NCDC and AM NIH will oversee the administration of coalition grants to 7 randomly-selected municipalities in each country (total of 14), execute population-level surveys in each of the 14 communities per country (total of 28), and facilitate coalition trainings, in partnership with Emory. TSMU/AUA will execute the evaluation of the coalitions by conducting baseline and follow-up assessments, in collaboration with Emory. [name], who has changed job positions since the start of the study and now is at George Washington University, will also be collaborating with Emory in this research study as an external investigator. However, George Washington University will not be recruiting any participants of their own or for their own research. The main study site will continue to be Emory University. [name] will be serving as the data collection coordinator at GWU, performing tasks such as programming web-based surveys. These activities will lead to the dissemination of significant research findings regarding the impact of coalitions on tobacco control and individual SHSe in LMICs and evidence-based practices for coalition activity. In conducting and disseminating the research, there will be significant research capacity-building within these organizations, as well as practice capacity-building within the local communities.

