Control Condition. The 14 communities assigned as controls will participate in the population-level survey and be provided with a site-specific summary of findings but will not participate in any aspects of the intervention. Additionally, to examine potential contamination in the control communities, a follow-up interview will be conducted with public health center leaders to assess any local coalition or grassroots actions regarding tobacco control that may have naturally occurred or be influenced by coalition activity in other communities.

Intervention Condition: Coalition Training, Development, and Action. Our intervention will test whether creation of local coalitions for

tobacco control is feasible in countries without a grassroots community-building tradition such as former Soviet Union countries, and if established, whether local coalitions can shift social norms regarding SHSe and promote adoption of smoke-free policies in public settings, specifically worksites and restaurants. Our intervention approach will be informed by the CCAT developed by Butterfoss and [name].²¹ CCAT posits that coalitions form due to a threat, opportunity, or mandate. In the current project, local public health centers will be the lead agency and play the role of convener of the coalition based on an opportunity (e.g., funding and participation in a major research project). In the

Figure 1. Conceptual Model for Creating and Enforcing Smoke-Free Policies at the Community Level in Georgia and Armenia

intervention communities, public health center staff will form a coalition by recruiting partner organizations from civil society and other government sectors (e.g., health care, education), conduct situational assessment, and develop and implement action plans to promote the adoption and enforcement of smoke-free policies in worksites and restaurants, settings selected based on general support for smoke-free policies in these settings^{19,20} and the likelihood of impacting population-level SHSe through widespread reach. The GE NCDC and AM NIH will establish subcontracts with the local public health centers in the randomly selected communities to provide funding for local staff to develop local coalitions and to support program activities (\$2,500 in Yrs 1 and 4, \$5,000 in Yr 2, \$7,500 in Yr 3, total=\$17,500/municipality).

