Year 1 Training: Situational Assessment. In Year 1, Drs. [name] and [name] will provide a protocol and materials to give an overview of the initiative and conduct training to build skills for how to conduct the situational assessment. The delivery of the training will be done by the Georgian NCDC and Armenian NIH staff in the respective countries to ensure translation to Georgian and Armenian as appropriate. [name] conducted a similar training on situational assessment for the China Tobacco Free Cities project.⁶⁵ See **Appendix B** for the presentation and tools (e.g., interview guide) that will be adapted for this training.

Year 2 Training: Coalition Building, Action Planning, and Strategy Selection. In Year 2, Drs. [name] and [name] will provide protocols and materials to conduct training regarding coalition building, action planning, and selecting intervention strategies. Each public health center will be asked to recruit at least eight coalition members and hold monthly meetings to lead the coalition through an action planning and implementation process. Situational assessment will inform which worksite and restaurant settings to target, as well as additional strategic settings. Action plans will include SMART (specific, measurable, achievable, realistic, and time-based) annual objectives, tasks, timelines, and persons responsible for completing each task. The training will include templates

and examples of action plans (*Appendix B*). We will provide examples of best practices in the US and elsewhere for creating policy change in each type of setting. [name] has taught community assessment, program planning, and evaluation to MPH students for 20 years, and was integrally involved in training CDC practitioners in China to conduct similar work.⁶⁵ The Emory Prevention Research Center, led by [name], also has such trainings for practitioners, which can be adapted for this project.

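### The two agencies that support the coalitions also collect the self-reported primary outcome, and the plan neither separates follow-up interviewers from that role, keeps the assignment from them, nor balances them within matched pairs

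*Combined protocol and SAP*

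**What the plan says.** **Coalition support.** Section C (Participants, setting, recruitment, and procedures) gives both jobs to the two agencies in one sentence. They are to "oversee the administration of coalition grants to 7 randomly-selected municipalities in each country (total of 14), execute population-level surveys" in all 28 communities, and to facilitate the coalition trainings with Emory. The rest of Section C adds detail:

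- Intervention Condition: "The GE NCDC and AM NIH will establish subcontracts with the local public health centers in the randomly selected communities to provide funding", at $17,500 per municipality in total.
- Year 1 Training: "The delivery of the training will be done by the Georgian NCDC and Armenian NIH staff in the respective countries".
- Technical assistance paragraph: "TA will be provided by the GE NCDC, AM NIH, and Emory research teams and will consist of monthly check-in e-mails or calls".

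**Outcome measurement.** Section C, Assessment 1, has the same agencies run both survey waves, in Year 1 and in Years 4/5. Section D, Assessment 1, says of the survey: "Data will be collected in person by NCDC/NIH staff using hard copy and/or technology-assisted procedures". The primary outcome is exposure to secondhand smoke as recalled by the respondent, including an index of exposed days in the past week by setting. The secondary outcomes include opinions on harm and on smoke-free rules.

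**Timing and adjustment.** Section C places randomization after the baseline survey. Section H (Aim 1, Analyses) adjusts for community baseline means.

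**Safeguards.** The protocol does not mention masking of interviewers, separation of survey staff from coalition-support staff, or allocation of interviewers within matched pairs. The staff-training topics in Section I do not include masking.

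**The concern.** Answers about recalled exposure and opinions can shift with how a question is put and followed up. An interviewer who has helped train or coach a coalition, or who knows which municipality has one, could probe differently in the two arms without intending to. The plan describes no biomarker, air measurement or other objective check that would show this.

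A difference of this kind would enter the comparison of arms at follow-up and would look the same as a real change in exposure or attitude. Section D itself expects that the impact on exposure may be modest, so a small reporting difference could matter to the conclusion.

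**Working it through.** **Step 1. Who does what.** Setting the sections of the protocol side by side:

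| Task | Who | Where | Communities |
|---|---|---|---|
| Administer and subcontract grants | NCDC, Armenian NIH | Section C | 14 intervention |
| Deliver or facilitate training | NCDC, Armenian NIH (with Emory) | Section C | 14 intervention |
| Monthly assistance | NCDC, Armenian NIH, Emory | Section C | 14 intervention |
| In-person survey, both waves | NCDC, Armenian NIH | Sections C and D | all 28 |
| Coalition assessments | TSMU/AUA (AUA and NCDC for the member survey in Section D) | Sections C and D | 14 intervention |

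The overlap is therefore between agencies. The text neither says nor rules out that the same individuals do both jobs. A separate evaluator is named for the coalition assessments but not for the primary outcome.

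**Step 2. Why baseline adjustment does not help.** No assignment exists when the baseline interviews are done, so the baseline means carry no arm-related interviewer effect. Write the follow-up difference between arms as the true effect plus b, where b is the arm-related reporting difference. Adjusting for baseline means removes differences already present at baseline. It leaves b in the intervention coefficient.

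**Step 3. Scale.** The documents give no value for b. The inputs from Section H are 14 communities per arm, 50 respondents each, ICC .10 and d = .35. Alpha and power for Aim 1 are not stated, so I assume two-sided alpha .05 and a normal test with no gain from matching or covariates.

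- Design effect = 1 + (50 − 1) × 0.10 = 5.9.
- Effective n per arm = 14 × 50 / 5.9 = 118.6.
- SE of the difference = √(2 / 118.6) = 0.130 SD.
- Check against the plan: power at d = .35 is 76.9%, and the effect detectable with 80% power is 0.364. That is close to the stated .35, so this SE is a fair yardstick.

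With no true effect, the chance of a significant result is 1 − Φ(1.96 − b/SE) + Φ(−1.96 − b/SE).

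- b = 0: 5%.
- b = 0.05 SD: b/SE = 0.385, giving 0.0576 + 0.0095, or about 6.7%.
- b = 0.10 SD: b/SE = 0.770, giving 0.1171 + 0.0032, or about 12%.

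At the lower ICCs that Section H also considers, the same two values of b give about 8% and 17% (ICC .05), or about 9% and 22% (ICC .03). By symmetry, a b of opposite sign gives the same rates, but the excess then lies on the side against the coalitions.

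**The case against.** The strongest reply is that the documents show shared institutions and not a compromised interviewer. Several stronger readings are tempting, and the text does not support them.

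- **That each interviewer has a stake in the result.** The protocol does not say that grant, training or assistance staff conduct interviews. An interest at agency level is a fair inference; a personal one is not documented. What stands is that the protocol leaves this open.
- **That the agencies award the grants.** They administer and subcontract them. Recipients are fixed by randomization, and Section C names an outside funder.
- **That bias would occur only in one arm and must favour the coalitions.** The same agencies interview in all 28 communities, so a general wish to please a health agency is present in both arms, and whatever is common to both cancels. An interviewer who knows the arm could also push control answers upward. Awareness campaigns could lead intervention residents to notice and report more smoke, which would work against a benefit.
- **That interviewers choose the households.** Section C describes a census-based frame, a random walk and Kish selection within households. It does not give interviewers the choice, and sampling discretion is a different issue from outcome reporting.
- **That question order needs a rule.** The survey items described in Section D contain no question about coalitions, so the documents show no order problem.

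It is also fair to say that separating staff within the same agencies does not change whose name is at the door. A respondent who wants to please NCDC or the Armenian NIH can still do so. The proposed change reduces the interviewer's contribution and leaves the respondent's.

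Two possible defences do not answer the point. That many analyses are led from another university does not protect data collection. Public campaigns make full masking unrealistic, but separating duties and balancing teams do not depend on full masking.

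**Conclusion.** The gap is real and limited. The plan permits staff who support the coalitions and know the assignment to conduct the follow-up interviews for a self-reported primary outcome, and it does not balance interviewers within pairs. Any resulting arm-related effect would arise only at follow-up, and the planned baseline adjustment would not remove it. Its most plausible direction favours the coalitions, but direction and size are both unknown, and zero is possible.

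The false-positive rates of about 6.7% and 12% rest on assumed differentials of 0.05 and 0.10 SD, no true effect, ICC .10 and two-sided alpha .05. They show how sensitive the comparison is. They do not estimate what is happening in this trial, and they do not measure what the fix would gain. The point justifies a clear improvement to the protocol, not a conclusion that the result will be biased.

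**What to change.** In Section D, Assessment 1, add that:

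1. follow-up interviewers are NCDC or Armenian NIH staff who have had no role in coalition grants, training or technical assistance;
2. they are not told the assignment;
3. the same interviewer team works both communities of each matched pair, so that a team's general interviewing style falls equally on the two arms.

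State as limitations that masking will be partial because coalition campaigns are public, and that respondents' wish to please the agency is not removed.

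The cost is less freedom in rostering; no extra interviews are needed. This assumes that each agency has survey staff with no coalition role, which the documents neither confirm nor deny. If such a separation already operates in practice, writing it down is enough.
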